5.3 Exclusion criteria

Exclusion criteria Modules 1-4: included students must not fulfil any of the following exclusion criteria:

- Refusal to participate by not providing signed consent and assent forms
- Having any medical condition that prevents them from washing their hands
- Having unexplained intermittent attendance in school (school teachers will be consulted and the school's absenteeism records will be checked for that)

- Not being at the same school for the course of the study (1 year)

Exclusion criteria Module 5: Refusal to participate by the student or his/her parents.

Exclusion criteria Module 6: Refusals to participate.

Exclusion criteria Module 7: Refusals to participate

5.4 Criteria for discontinuation of study

5.4.1 Discontinuation of individual participants

A participant can be discontinued from the study for the following reasons:

1. Withdrawal of informed consent
2. Moving from the included school to another school
3. Long-lasting absence of at least 6 months
4. Death
5. Inaccessibility of the school due to a high risk security situation

6 STATISTICS

6.1 Hypothesis

6.1.1 Primary hypothesis

The primary hypothesis stems from the research question: Does the H4H MCI make a difference in the hand hygiene of primary school students in Nigeria and Palestine?

$H_{1,1}$ = There is a difference in hand hygiene between the intervention and control groups of primary school students in Nigeria and Palestine.

$H_{0,1}$ = There is no difference in hand hygiene between the intervention and control groups of primary school students in Nigeria and Palestine.

6.1.2 Secondary hypotheses

Depending on the secondary objective, different secondary hypotheses were formed:

$H_{1,1}$ = There is a difference in well-being between the intervention and control groups of primary school students in Nigeria and Palestine.

$H_{0,1}$ = There is no difference in well-being between the intervention and control groups of primary school students in Nigeria and Palestine.

$H_{1,2}$ = There is a difference between hygiene-related RANAS variables between the intervention and control groups of primary school students in Nigeria and Palestine.

$H_{0,2}$ = There is no difference between hygiene-related RANAS variables between the intervention and control groups of primary school students in Nigeria and Palestine.

$H_{1,3}$ = There is association between personal, physical and social contextual factors and hand hygiene and the well-being of primary school students in Palestine.

$H_{0,3}$ = There is no association between personal, physical and social contextual factors and hand hygiene and the well-being of primary school students in Palestine.

$H_{1,e}$ = There is a difference in hygiene-related health outcomes and absenteeism between the intervention and control groups of primary school students in Nigeria and Palestine.

$H_{0,e}$ = There is no difference in hygiene-related health outcomes and absenteeism between the intervention and control groups of primary school students in Nigeria and Palestine.

6.2 Determination of sample size

The number of clusters (schools) and students per school was assessed by simulations using the software R aiming for a power of 80% at the 95% confidence level. The Intraclass Correlation Coefficient (ICC) was assumed at 0.2. The simulation assumed a prevalence of handwashing occurrence before eating during the time of observation (3 hours) taking place over one day of 20% in control vs 45% in intervention schools after 1 year from the baseline. Based on this assumption, 13 schools are needed per arm with 50 students per school. However, the number of students assessed for different modules will differ due to the capacity limitation of assessing the 50 students included in each school.

For Module 1, only 25 students randomly selected out of the 50 students randomly selected from the classes included in the intervention in each school will be targeted. For Modules 2 and 4 the 50

students randomly selected from the one or two classes included in the intervention in each school will be targeted. For Module 3 only 12 students randomly selected out of the 25 students involved in module 1 in each school will be targeted. For Module 5, all students in the the classes included in the intervention in each school will be invited to participate by delivering a survey to be reported by one of their parents. For Module 6, 10 gender-separated FGDs will take place in the included schools in the intervention arm; 5 FGDs for each gender. In addition, 5 FGDs targeting teachers will be conducted. For Module 7, 10-20 interviews will be conducted.

6.3 Description of statistical methods

Baseline characteristics will be summarized using descriptive statistics. The difference in the observed proportion of washing hands before eating between two study arms at follow-up will be investigated using logistic mixed effect regression to adjust for potential correlation within schools. In the primary analysis only the intervention will be included as predictor and school as a random effect.

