2.3 The hands4health project

This project is funded by the Swiss Development Cooperation (SDC) (<https://hands4health.dev/>) and aims to increase hygiene in schools without any direct access to water in the context of humanitarian crises. The project has a strong focus on the Sustainable Development Goal (SDG) 6, clean water and sanitation. In addition, the SDG 1 (no poverty), SDG 3 (good health and wellbeing), SDG 4 (quality education), SDG 5 (gender equality), SDG 10 (reduced inequalities), and SDG 11 (sustainable cities and communities) are targeted (Pradhan *et al.* 2017). The project is led by 10 partners from academia, non-governmental organizations (NGOs), and the private sector. To increase the level of hygiene, an intervention package consisting of (i) a handwashing station called Gravit'ea (only in Nigeria), (ii) rehabilitation of WASH infrastructure (only in Palestine) (iii) a behaviour change intervention from Ranas Ltd., a spin-off company of the Swiss Federal Institute of Aquatic Science and Technology (Eawag), (iv) training for monitoring residual chlorine in water storage by Fachhochschule Nordwestschweiz (FHNW) (only for Palestine), (v) capacity development on O&M and overall management by Fachhochschule Nordwestschweiz (FHNW), and (vi) the management of WASH infrastructure at facilities, including water storage, water distribution, handwashing and sanitation by FHNW. The Gravit'ea is designed by Gravit'ea Association, and evaluated by FHNW previously together with Gravit'ea and will be tested by the FHNW with filters supplied from the company Martin Systems. The Ecole Polytechnique Fédérale de Lausanne (EPFL) will test different greywater disinfection methods. The behavioural change intervention will be designed and lead by Ranas Ltd. The NGOs Terre des hommes (Tdh) and Cesvi will support the intervention and all data collection with local teams and expertise in Nigeria and Palestine, respectively. The Swiss Tropical and Public Health Institute (Swiss TPH) will lead the efficacy assessment of the project. The Palestinian Polytechnic University (PPU) and the University of Maiduguri (UNIMAID) have leading roles in the technology evaluation and user-centered design for local context; impact evaluation; water quality analysis, data collection and analysis; and quality control. Skat Foundation will coordinate the development of a systematic approach to facilitate handwashing in institutional settings, as well as develop an overall Theory of Change (ToC) for the intervention and a stakeholder engagement strategy. The ToC process, which will be continued throughout the project duration, and the systematic approach are directly related – both processes provide feedback to each other. One of the main results will be a Theory of Action (ToA), which will help the field and project teams to plan and implement their activities in a strategic and targeted way. The ToC aims to help local teams and the researchers to understand how the local WASH system works in schools in Nigeria and Palestine, and to identify the interplay of actors and factors that shape the overall system dynamic.

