2.3.2 Rehabilitation of WASH infrastructures

At an early stage of the H4H project, it became clear that the implementation of the Gravit'eau devices in Palestinian schools is not culturally acceptable. The Palestinian Ministry of Education refused to use recycled water due to social and administrative obstacles. Alternatively, different rehabilitation works will take place in the schools according to each school need. These activities include, construction of drinking stations, rehabilitation of toilets and handwashing stations, installing water-saving taps and installing soap dispensers at drinking and handwashing stations.

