Knowledge about the effectiveness of hand hygiene campaigns in the context of humanitarian emergencies is extremely scarce due to the lack of baseline data and monitoring and evaluation activities (Vujcic *et al.* 2014, Als *et al.* 2020). In conflict settings, hand hygiene is mostly being investigated in community settings, but not in schools where infections can easily spread (Als *et al.* 2020, Domini *et al.* 2020). In addition, data mainly relies on self-reporting and can therefore rarely be triangulated. Moreover, information about barriers and motivators of handwashing campaigns in emergency settings is scarce (Vujcic *et al.* 2014). Finally, data on handwashing interventions in complex emergencies is rarely shared publicly and therefore is not being used to inform other handwashing campaigns (Vujcic *et al.* 2014).

The Gravit'eau handwashing station is a promising invention to increase access to water in settings suffering water scarcity and humanitarian crises. However, its impacts on health determinants and outcomes of its users have to date never been assessed in a real-world setting over long time periods (Gravit'eau 2022). For scaling up the use of Gravit'eau, scientific evidence about its impact and potential barriers to implementation are much needed.

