4 STUDY DESIGN

The overall project will follow a multi-center cluster-randomized controlled trial (cRCT) design (Figure 2). Prior to this study, a group of schools in the study's target areas were surveyed by the Tdh (in Nigeria) and Cesvi (in Palestine) using the Facility Evaluation Tool for WASH in Schools ([FACET WINS](#)) which is a monitoring tool for WASH delivery services in schools. From these schools a subsample was identified which fulfils certain inclusion criteria (for the inclusion criteria see chapter 5.2 Inclusion criteria).

This subsample was handed over to the local Tdh and Cesvi collaborators who carefully assessed the security situation around the schools. The Tdh and Cesvi collaborators then selected 26 facilities per country, which are most probable to still be accessible for data collection within the next year. These 26 schools will then be allocated to the two arms (intervention vs. control) with covariate constrained stratified randomization using computer-generated randomization code provided by a statistician not involved in any field activities. The intervention arm will receive the full intervention package (handwashing station, behavioural change intervention, capacity development, and management support). The control arm will receive nothing for the duration of the intervention (12 months). Afterwards, they will receive the same intervention package with potential improvements identified in the former intervention group.

In the selected schools, 50 eligible students from each school will be selected from one or two classes within the age group (10-12 years) using random sampling. If the school has at least one class that has ≥ 50 students within the target age group, the sample will be selected from that class, otherwise, the sample can be selected from two classes. For module 1, only 25 students of the 50 students included in the study in each school will be involved. For module 2, the 50 students included in the study in each school will be targeted for assessment using this module. For Module 3, 12 students out of the 25 students targeted with assessment using module 1 will be targeted for assessment using this module.

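### The intervention hardware differs between Nigeria and Palestine, but the primary model has no country term, no country-specific effect is planned, and the plan does not say whether the model is pooled

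*Combined protocol and SAP*

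**What the plan says.** On the primary model, section 6.3 has: "In the primary analysis only the intervention will be included as predictor and school as a random effect". The statistical row of the synopsis says the same. Section 6.3.1.2 adds a secondary adjustment for known confounders and imbalanced predictors, but does not name country.

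On the intervention, section 2.3 lists the Gravit'eau station for Nigeria only, and next to it "ii) rehabilitation of WASH infrastructure (only in Palestine"). Residual-chlorine training is also for Palestine only. Section 2.3.2 explains the split: using the Gravit'eau "devices in Palestinian schools is not culturally acceptable", so schools there receive works according to need, such as drinking stations, rehabilitated toilets and handwashing stations, water-saving taps and soap dispensers. Behaviour change, capacity development and management support are common to both countries. Section 4 nevertheless describes a single package: "The intervention arm will receive the full intervention package (handwashing station, behavioural change intervention, capacity development, and management support").

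On the aim, the primary hypothesis in section 6.1.1 covers both countries together: "There is a difference in hand hygiene between the intervention and control groups of primary school students in Nigeria and Palestine". The rationale in section 3.1.1 says of the Gravit'eau station that "scientific evidence about its impact and potential barriers to implementation are much needed".

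On the number of schools, the synopsis gives 26 in total with 1300 students, and section 4.4 refers to 13 intervention schools. Section 4 says that 26 facilities were selected in each country.

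**The concern.** One treatment indicator stands for two different sets of hardware. If the model is fitted once to all schools, its single odds ratio averages over both. A positive result could then come from one country while the other gained little, and nothing pre-specified would show it. Palestinian schools have no Gravit'eau station, so they carry no information on it, although evidence for its scale-up is one of the stated reasons for the project.

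The plan gives grounds to expect unequal effects. Class sizes differ (51 to 101 in the Nigerian schools, section 3.2; about 30 in the Palestinian ones). Nigerian pupils are drawn from classes near the station (section 5.2). The Module 5 text in section 4 says that contextual factors may modify effectiveness.

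Because the plan does not say whether the model is pooled or fitted per country, that choice could also be made after the data are seen.

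**Working it through.** **Inputs.** Section 6.2: 20% v 45%, 13 schools per arm, 50 students per school, "aiming for a power of 80% at the 95% confidence level", and "The Intraclass Correlation Coefficient (ICC) was assumed at 0.2". Assumptions: a two-sided test (not stated, but the hypothesis is non-directional); the ICC applies to the proportion scale (not stated); the same rates and ICC in both countries; an even split of schools if 26 is the overall total.

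**1. The plan's own figure.**
- Two proportions, 20% v 45%, two-sided 0.05, 80% power: 54 students per arm without clustering.
- Design effect: 1 + (50 − 1) × 0.2 = 10.8.
- 54 × 10.8 = 583.2 students; 583.2 / 50 = 11.66, so 12 schools per arm. Adding the customary one cluster per arm gives 13, as stated.
- Power at 13 per arm is about 83% (noncentral t, 24 df).

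So 13 per arm is the size of one two-arm comparison. It fits one trial across both countries (synopsis) or one complete trial in each (section 4).

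**2. What an average can hide (illustration, not a forecast).** With equal school numbers, 20% to 60% in one country and 20% to 30% in the other are gains of 40 and 10 points. Their mean is (40 + 10) / 2 = 25 points, exactly the planned difference.

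**3. Precision within one country.** Variance of a school's proportion: p(1 − p) × [0.2 + 0.8/50] = p(1 − p) × 0.216.
- Control: 0.16 × 0.216 = 0.0346. Intervention: 0.2475 × 0.216 = 0.0535. Sum before rounding: 0.0880.

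| Reading | Schools per arm per country | SE | t quantile (df) | 95% half-width | Interval around 25 points |
|---|---|---|---|---|---|
| 26 schools per country | 13 | √(0.0880/13) = 0.082 | 2.064 (24) | about 17 points | about 8 to 42 |
| 26 schools in total | 6.5 | √(0.0880/6.5) = 0.116 | 2.201 (11) | about 26 points | about −1 to 51 |

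A normal quantile of 1.96 would give 16 and 23 points, which is optimistic with so few clusters.

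**4. Power.** Within one country, for 20% v 45% (noncentral t): about 83% with 13 per arm; about 46% to 54% with 6 to 7 per arm.

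For the arm-by-country difference (normal approximation, risk-difference scale), the SE is √2 times the country SE: 0.116 or 0.165. Power is Φ(d/SE − 1.96):

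| True difference between country effects | 26 schools per country | 26 in total |
|---|---|---|
| 10 points | 14% | 9% |
| 20 points | 40% | 23% |
| 25 points | 57% | 33% |

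An interaction test alone therefore cannot settle whether the effects are alike. The estimates and their intervals have to carry the information.

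**5. Error rate if either country could count as success.** Two independent tests at 0.05 give 1 − 0.95² = 9.75%, so country results need a stated status.

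**The case against.** There are four fair points in favour of the plan.

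- **Pooling is not stated.** Section 4 selects 26 facilities per country and then allocates these 26 to two arms, which matches the calculated size for one complete trial. The Figure 2 caption speaks of the trial in Nigeria. On that reading the section 6.3 model could be run in each country and would give country effects. This stands as far as it goes: a reader might take it as settled that the plan pools, and the documents do not say so. But the title, the single hypothesis, the synopsis total of 26 and the 13 intervention schools in section 4.4 make one pooled trial the more natural reading. The ambiguity is itself something to fix.
- **No objective is left unanswered.** A reader might infer that the pooled effect fails a country objective. The documents contain none: section 3.1.2 and section 6.1.1 ask about the package in both countries together, and a pooled effect answers that.
- **Evidence on Gravit'eau is rationale, not an objective.** No arm isolates the station, so even a Nigeria-only estimate is the effect of the station together with the other components. A country split would help with that need without fully meeting it.
- **An average effect of a locally adapted package is a legitimate target.** Palestinian works vary between schools, so a country split does not give a uniform package either. The generic handwashing station in section 4 could also cover rehabilitated ones. This supports keeping the overall effect as the primary test. It does not explain why no country effect is planned when the main hardware differs.

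**Conclusion.** The concern holds in a limited form. Hardware differs by country, the stated model has no term for country, and no country-specific effect is planned. If the trial is analysed as one, the result is a valid average for the primary objective as worded, but it does not show what either package achieved. Whether the model is pooled must be stated, and the conflicting school counts must be reconciled.

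In size, a country estimate around the planned 25 points would carry a half-width of about 17 points with 26 schools per country, and about 26 points with 26 in total. The second interval would include zero. These figures rest on the assumptions listed with the calculation. If the ICC of 0.2 is on the latent scale, simulated power at 13 per arm is about 93% to 94%, and the intervals would be narrower.

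A reader might go further and infer that the sponsor will present a positive result as proof for the station. Nothing in the documents commits to such a claim. The point is that the plan does not yet limit what may be concluded.

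**What to change.** - **Section 6.3:** state that the single primary test is the overall intervention effect from the pooled model, with country added as a fixed effect and school as a random effect.
- **Supportive analysis:** pre-specify a separate model with an arm-by-country term, and report the effect with its 95% interval in each country, using small-sample degrees of freedom. It should not replace the primary model, because under usual coding the arm coefficient would then be the effect in the reference country only. State that a non-significant interaction is not evidence of equal effects, and that success will not be claimed from one country alone.
- **School counts:** reconcile the synopsis and section 4.4 with section 4.
- **Section 4:** describe the two packages separately.
- **Conclusions:** limit statements about Gravit'eau to the Nigerian package (station plus behaviour change, capacity development and management), not the station alone.

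The cost is a change of wording and one further model on data already to be collected, with no added schools or visits. The downside is wide country-specific intervals, especially with only 26 schools in total, and a more limited headline claim.

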
Measurements and Procedures
	
Different methods across modules will be used to achieve the objectives of this project. These modules will include qualitative and quantitative data approaches in order to enable a triangulation of the overall project results. The following modules will be used in the cRCT and the overall project: (i) Module 1: A combined RANAS and wellbeing survey, (ii) Module 2: Structured handwashing observations, (iii) Module 3: Microbiological analysis of hand rinse samples, (iv) Module 4: Diary approach for pre-defined health outcomes and absenteeism incidence, (v) Module 5: personal, physical, and social contextual factor survey, (vi) Module 6:FGDs and (vii) Module 7: Key informant interviews (KII).
 
Endpoints of Modules 1-3 will be assessed at baseline, at follow-up and endline of the cRCT. Module 4 will be used to collect data longitudinally over the course of 12 months. Module 5 will be assessed at baseline and only in Palestine, Module 6 and 7 will be used in the middle of the intervention phase in the intervention groups.

Number of Participants with Rationale (if no Power Analysis conducted)
	
The sample size calculation yielded that 13 schools are needed per arm with 50 students per school. With political instability and other factors which might lead to a loss of follow-up, we have 7 schools as backup schools. This will lead to 26 schools in total with a total number of 1300 students. The number of students participating in different modules will differ due to the capacity limitation of assessing the 50 students included in each school. For module 1, only 25 students of the 50 students included in the study in each school. For module 2, the 50 students included in the study in each school will be targeted for assessment using this module. For Module 3, 12 students out of the 25 randomly selected students to be targeted with RANAS and well-being survey will be targeted for assessment using this module.

	
Module 4 follows the sample size calculation of the cRCT design, hence 50 students from each of the 26 schools will be monitored. For Module 5, all students in the included classes in each school in Palestine will be delivered a survey to be self-reported by their parents. For Module 6, 10 FGDs (including students) and 5 FGDs (including teachers) will be administered and for Module 7, 10-20 interviews.

Study Duration	14 months

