Study Schedule	
For Nigeria: May 2023 of First-Participant-In July 2024 of Last-Participant-Out
 
For Palestine: March 2023 of First-Participant-In May 2024 of Last-Participant-Out

Investigator(s)	
[name]. [name] Swiss Tropical and Public Health Institute [name] [contact] [contact]
 
PhD candidate (research assistant) under supervision of [name]. [name]: [name] Swiss Tropical and Public Health Institute [name], Switzerland [contact]
 
[name] Terre des hommes Nigeria [name] [contact], [name] [contact]
 
[name] Project coordinator Cesvi Palestine [name] [name] [contact]
 
[name] Junior Programme Officer Skat Foundation [name] [contact] [contact]

Study Centre(s)	Nigeria and Palestine
Statistical Analysis incl. Power Analysis	The number of clusters (schools) and students per school were calculated using the software R with a power simulation of 80% developed by [name]. The Intraclass Correlation Coefficient (ICC) was assumed at 0.2. The simulation assumed a prevalence of handwashing occurrence before eating during the time of observation (3 hours) taking place over one day of 20% in control vs 45% in intervention schools after 1 year from the

	
baseline. Based on this assumption, 13 schools are needed per arm with 50 students per school.
 
The baseline data will be reported descriptively. The imbalance at baseline between trial arms will be assessed in terms of clinical importance rather than in terms of statistical significance. The intervention effect will be estimated with logistic mixed effect regression to adjust for potential correlation within schools. For the primary analysis, the model will include only the outcome (handwashing occurrence before eating during the time of observation (3 hours) taking place over one day and assessed at the endline) and the intervention as a predictor and school as a random effect. Further analyses will include known confounders and variables imbalanced at baseline. All analyses will use the available case population. No imputation of missing data will be done because loss to follow-up is usually small to moderate in school-based studies.

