Module 2: Structured handwashing observations: Structured handwashing observations are perceived as a gold standard method to assess handwashing behaviour in schools (Pickering *et al.* 2013; Caruso *et al.* 2014; Dreibelbis *et al.* 2016; La Con *et al.* 2017; Parkinson *et al.* 2018). Data from Module 1 and the observations can later be combined through a unique ID of the study participants. The observations will be administered with students three times at the same time points as the survey in Module 1. To be able to assess individual behaviours and link them to data collected using other tools, all eligible students in the classes selected for the study will be assigned coloured badges with their unique IDs. Students will be informed that they are randomly assigned the colours. However, the data collector will agree with the school teachers on a specific colour to be assigned for the 50 selected students for the study. The observation will start at 9:00 am (60 minutes before the breakfast break) and end at 12:00 pm (90 minutes after the break). The data collector will pilot the observation process before the intervention and in coordination with the school staff.

The occurrence of handwashing with soap will be observed for each of the two critical handwashing events (after using the toilet and before eating) for each included student. The occurrence of handwashing before eating (our primary outcome) is an opportunity that could be observed once for all students when break time starts. The break time included in the observation period is the first break for all students during a school day, and all of them use it for eating their brunch (as confirmed by the local teams). No matter where the station is they are expected to come and wash their hands before eating. For observing the occurrence of the other critical event and if the station was not located next to toilets, we would have two observers; one is next to toilets and the other one is next to the stations. Both would observe and then compare their results. The observations will result in a dichotomous measure, i.e. if the handwashing with soap for each critical event occurred or not. However, there will be choices like "was not visible" or "soap or water was not available" to take into consideration the complicated conditions in the field.

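### The primary model omits baseline handwashing, which is already observed in the same pupils with the same tool: lost efficiency of uncertain size, not bias or a power shortfall.

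*Combined protocol and SAP*

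**What the plan says.** Section 6.3 defines the primary model: "In the primary analysis only the intervention will be included as predictor and school as a random effect". The Synopsis (Statistical Analysis) agrees: "For the primary analysis, the model will include only the outcome", followed by the endline outcome, the intervention as predictor and a random effect for school. Baseline data are to be reported descriptively. Section 6.3.1.2 and the Synopsis add a secondary analysis that adjusts for confounders already known and for variables found unbalanced at baseline. Neither place names baseline handwashing.

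The baseline value of the primary outcome is nevertheless collected. The Synopsis (Measurements and Procedures) says "Endpoints of Modules 1-3 will be assessed at baseline, at follow-up and endline of the cRCT". Section 4, Module 2, says "The observations will be administered with students three times at the same time points as the survey in Module 1". Pupils carry unique IDs (section 4, Module 2) and must stay in the same school for the year (section 5.2), so this is a closed cohort.

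Section 6.2 gives the design inputs: "aiming for a power of 80% at the 95% confidence level", "The Intraclass Correlation Coefficient (ICC) was assumed at 0.2", "20% in control vs 45% in intervention schools after 1 year from the baseline", and the result "13 schools are needed per arm with 50 students per school". No baseline term is mentioned there.

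**The concern.** With an ICC of 0.2 and 50 pupils per school, nearly all the error in the arm comparison is variation between schools. A school's own baseline handwashing is the natural measure of that variation. It costs nothing extra, because the baseline round is already planned. The plan gives no reason for leaving it out.

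The secondary analysis does not secure its use. It does not name the variable, and part of the covariate choice waits on an imbalance judged by clinical importance (Synopsis). Section 4.3 says that the statistician cannot be blinded, so that judgement would be made by someone who knows the allocation. Pre-specification removes the discretion.

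At stake are precision and, if the arms differ by chance at baseline, part of that difference appearing in the primary estimate.

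**Working it through.** **Inputs from section 6.2.** 20% vs 45%; ICC 0.2 (scale not stated, taken here as the proportion scale); 50 pupils per school; 13 schools per arm; 5% level, read as two-sided. **Assumed, because the documents do not give it:** the correlation r between a school's baseline and endline proportions.

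**1. The plan's own figure.** The variance of a school proportion is p(1−p)[ICC + (1−ICC)/50] = p(1−p)(0.200 + 0.016) = 0.216·p(1−p). The between-school part is 0.200 of 0.216.

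The variance of the arm difference is (0.20×0.80 + 0.45×0.55)×0.216/13 = 0.4075×0.216/13 = 0.00677, so the SE is 8.23 percentage points. The noncentrality is 25/8.23 = 3.04. With 24 df, power is **83.0%**; with 12 schools per arm it is 79.7%. Thirteen is therefore the smallest number that reaches 80%, and the planned size reproduces without any baseline term. A simulation of the planned logistic mixed model gave about 78% at 13 per arm.

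**2. Adding the school's baseline proportion.** The variance is multiplied by 1 − r², with 23 df.

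| Assumed r | Variance factor | SE (points) | Formula power | School-level simulation, unadjusted to adjusted |
|---|---|---|---|---|
| 0 | 1.00 | 8.23 | 82.9% | loss of about 2 points |
| 0.3 | 0.91 | 7.85 | 86.2% | 82.0% to 82.5% |
| 0.5 | 0.75 | 7.13 | 91.9% | 81.5% to 87.5% |
| 0.7 | 0.51 | 5.88 | 98.3% | 81.3% to 95.0% |

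The simulated gains are smaller partly because 50 pupils per school blur the correlation. In one set of 1,500 simulated trials per setting, correlations of 0.3, 0.5 and 0.7 between underlying school prevalences became about 0.25, 0.43 and 0.63 between observed proportions. Type I error stayed near 5% (4.8% unadjusted, 4.5% adjusted).

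**3. The planned model itself.** Simulating the logistic mixed model (286 trials per setting, Monte Carlo error about 2 points) gave about 77% to 78%, 79% to 85% and 79% to 93% at school-level correlations of 0.3, 0.5 and 0.7. At zero correlation power fell from about 78% to 73% (886 trials).

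**4. Conditions that shrink the gain.**
- Correlation 0.5 in control schools but 0 in intervention schools: 81.8% to 83.0%. With 0.3 and 0: 82.5% to 81.8% (4,000 simulated trials each).
- Baseline prevalence of only 5%, correlation 0.5: 81.7% to 85.5%.
- ICC of 0.2 on the logit scale, correlation 0.5: about 93% to 96%.
- 26 schools per country pooled, so 26 per arm: 98.8% unadjusted by the formula in step 1, leaving almost nothing to gain.

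**5. School or pupil baseline?** Let the school-level and pupil-level correlations contribute to r with weights 50×0.2/(1+49×0.2) = 10/10.8 = 0.926 and 0.8/10.8 = 0.074. Nearly all the information is at school level.

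**6. Chance imbalance.** If baseline prevalence is 20% with the same ICC, and handwashing is not balanced by design, the arm difference at baseline has SD √(2×0.16×0.216/13) = 7.3 points. The unadjusted estimate moves by slope × imbalance. At r = 0.5 the slope is 0.5 in control schools (0.5×√(0.16/0.16)) and 0.62 in intervention schools (0.5×√(0.2475/0.16)), so a one-SD imbalance moves the estimate by about 3.6 to 4.5 points. At r = 0 it moves it by nothing.

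**The case against.** The case for leaving the plan alone is substantial. A pre-specified, unadjusted endline comparison is valid, the sample size never relied on a baseline term, and an adjusted analysis is already planned. All of that stands. It limits the point to efficiency.

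The gain also rests on a correlation that the documents do not give, and there are reasons to expect a weak one in the intervention arm. Schools were chosen for lacking a directly connected water source (section 5.2). The intervention then installs stations in Nigeria, or rehabilitates handwashing points and adds soap dispensers in Palestine (sections 2.3 and 2.3.2). Baseline handwashing with soap may sit near the floor. The fallback snack scenario in Module 2 could make rounds less comparable if only some rounds use it. This stands too, and is why the size is given as a range that includes no gain and a small loss.

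The number of schools is unsettled: the Synopsis gives 26 in total, section 4 gives 26 per country. Pooling on the second reading removes most of the benefit.

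A reader might infer that a baseline imbalance passes straight into the primary estimate. It does so only in proportion to the correlation. Allocation is also constrained and stratified to balance baseline characteristics (sections 4 and 4.3), and in Palestine the baseline assessment precedes randomisation (section 4, Module 5). The balancing variables are not named, so this mitigates the concern without removing it.

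**Conclusion.** The omission is clear from the text, and pre-specifying the covariate is worthwhile. Confidence is high on the omission and low on the size of the gain. On the planned 13 schools per arm, with the ICC on the proportion scale, adjustment adds between almost nothing (correlation 0.3) and about 13 to 15 points of power (correlation 0.7). At 0.5 the gain is about 6 points in school-level simulation and 9 by formula. If baseline is uninformative, the loss is about 2 points in school-level simulation and about 5 in mixed-model simulation.

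Three stronger readings are not supported:
- **That the trial is underpowered or its analysis biased.** Thirteen schools per arm reproduces without a baseline term, and the unadjusted comparison is unbiased on average over randomisation.
- **That the odds-ratio interval must become narrower.** The smaller SEs above are on the risk-difference scale. In a logistic mixed model the adjusted odds ratio is conditional on baseline and its SE need not shrink; the benefit appears as power.
- **That each pupil's own baseline result is also needed.** It carries little of the information, adds parameters, and would drop pupils without a baseline observation under the available-case rule unless a missing category were added.

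**What to change.** In section 6.3 and in the Synopsis, specify that the primary logistic mixed model contains the intervention, the school's baseline proportion of observed pupils washing with water and soap before eating as one fixed covariate, and a random intercept for school. State that the covariate is included regardless of observed imbalance, and that the intervention odds ratio is conditional on it. Keep the unadjusted model as a sensitivity analysis. Leave the pupil-level baseline term out.

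Because the covariate is a school value, no pupil is lost under the available-case rule for lacking an individual baseline observation, provided that the school had a baseline round.

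The cost is a sentence or two in each place and one degree of freedom, with no new data. The downside is the small loss of power if baseline turns out not to predict endline.
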